#### **4.6.2 Safety evaluation**

All tables, figures and listings in this section will be presented for the SAF analysis set.

##### **4.6.2.1 Adverse events**

Adverse events (AEs) are to be recorded during the whole study period.

AEs are coded according to Novartis MedDRA, Version 24.1.

The AE data will be listed, sorted by site code, patient number, and preferred term. This list will include: adverse event, MedDRA system organ class, MedDRA preferred term, start date, stop date, intensity, outcome, relationship to study drug, action taken, and a variable indicating whether an AE was considered a serious adverse event (SAE).

AEs starting prior to start of treatment will not be included in the summary tables, but listed only.

A general summary table of AEs will contain the total number of AEs, the total number of SAEs, and separate descriptions of the splits for the variables relationship to study drug, action taken,

outcome and intensity. Outcome is categorized according to the CRF as “resolved” (i.e. resolved completely or resolved with sequelae), “ongoing”, “fatal” or “unknown”.

The incidence of an AE is defined as the number of patients who experience that event, divided by the number of patients in the SAF population. With AE incidence, each event will be counted only once for a given patient. More specifically, if a patient reports the same event more than once, as determined by preferred term and system organ class, that patient will be counted only once for the incidence of the AE. For example, when a patient reported three instances of headache, this patient counts only once towards the total incidence of headache. Incidence of events within a system organ class is defined similarly. Whenever incidence is cross-tabulated with intensity in the summary tables, the incidence of an AE will be calculated for each level of intensity, i.e., the number of patients who experience that AE on a certain level of intensity.

Incidence tables will provide information about rates of AEs per patient-year, calculated as  $\{(number\ of\ patients\ who\ experience\ that\ event)\ / (years\ of\ exposure)\}$ . Additional tables will enable a direct comparison of formulation specific rates of events per patient year.

The occurrence of an AE is defined as the total number of times the event occurs in the SAF population. With AE occurrence, a patient may contribute more than once to the total occurrence count. More specifically, if a patient reports a particular event, as determined by preferred term and system organ class (and having removed duplicate reporting of the same event, as described above) more than once, each event will count once towards the total event occurrence. Using the above example, headache would be counted three times for the patient who reported three separate occurrences of headache.

Occurrence tables will provide information about rates of AEs per patient-year, calculated as  $\{(number\ of\ events)\ / (years\ of\ exposure)\}$ . Additional tables will enable a direct comparison of formulation specific rates of events per patient year.

The incidence and occurrence of each AE will be reported by MedDRA system organ class and preferred term, cross-tabulated with the intensity, action taken, and outcome. Additionally, total incidence and occurrence will be provided for each system organ class.

The whole set of AE summary tables will be produced for all AEs and separately for adverse drug reactions (ADR), serious AEs and serious ADRs. Adverse events will be considered as adverse drug reactions if a causal relationship to the study drug is suspected by the investigator.

For the Final CSR and registry purposes a summary of non-serious AEs by SOC, PT and intensity is required in addition.

AEs of special interest are defined as intracranial haemorrhage and intracranial aneurysm and possible drug interaction with sex steroids, corticosteroids, anticonvulsants and cyclosporine.

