  - Suspected: The temporal relationship of the clinical event to trial drug administration makes a causal relationship possible, and other drugs, therapeutic interventions or underlying conditions do not provide a sufficient explanation for the observed event.
  - If the event is due to lack of efficacy or progression of underlying illness (i.e. progression of the study indication) the assessment of causality will usually be 'Not suspected'. The rationale for this guidance is as follows:
    - the symptoms of a lack of efficacy or progression of underlying illness are not caused by the trial drug, they happen in spite of its administration
    - both lack of efficacy and progression of underlying disease can only be evaluated meaningfully by an analysis of cohorts, not on a single subject
- its duration (start and end dates) or 'ongoing' at the 30 day safety follow-up /end of study visit
- whether it constitutes a serious adverse event (SAE) (see Section 7.4.8 for the definition of SAE)

**Unlike routine safety assessments, SAEs are monitored continuously and have special reporting requirements; see Section 8.1**

- action taken: All adverse events must be treated appropriately. Treatment may include one or more of the following: no action taken (i.e. further observation only); study drug dosage adjusted/temporarily interrupted; study drug permanently discontinued due to this adverse event; concomitant medication given; non-drug therapy given, subject hospitalized/subject's hospitalization prolonged.
- Its outcome (not recovered/not resolved; recovered/resolved; recovering/resolving, recovered/resolved with sequelae; fatal; or unknown)

Once an adverse event is identified, it must be followed until its resolution or until it is judged to be permanent, and assessment must be made at each visit (or more frequently, if necessary) of any changes in severity, the suspected relationship to the study drug, the interventions required to treat it, and the outcome.

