#### **10.4.4 (Serious) Adverse Events / Incidents**

Adverse events will be coded using MedDRA (Version to be determined depending on the time of the analysis). The number and percentage of patients having at least one (serious) adverse event will be tabulated. The (serious) adverse events will be displayed by system organ class and preferred term and the relationship to the study drug, intensities and outcome will be shown in corresponding frequency tables.

Since incidents are qualified as clinical SAEs they are handled in the same way as all other clinical SAEs. A near incident is handled as a clinical SAE in case of seriousness, otherwise as an adverse event.

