**FIGURE 14.2-2.21 Mean IGF-1 SDS serum levels over time, means  $\pm$  95% CI (FAS)**

**FIGURE 14.2-2.22 Mean IGFBP-3 SDS serum levels over time, means  $\pm$  95% CI (FAS)**

**5.4 Safety Tables including shells**

**TABLE 14.3-1.1 GENERAL SUMMARY OF ADVERSE EVENTS (SAF)**

		Number of patients (%) (N=277)	Number of adverse events (%)
Any adverse events	XXX	(XX.X%)	XXX
Relationship to study drug			(XX.X%)
Not suspected	XXX	(XX.X%)	XXX
Suspected	XXX	(XX.X%)	XXX
Missing	XXX	(XX.X%)	XXX
Intensity			(XX.X%)
Mild	XXX	(XX.X%)	XXX
Moderate	XXX	(XX.X%)	XXX
Severe	XXX	(XX.X%)	XXX
Missing	XXX	(XX.X%)	XXX
Serious adverse event			(XX.X%)
No	XXX	(XX.X%)	XXX
Yes	XXX	(XX.X%)	XXX
Missing	XXX	(XX.X%)	XXX
Outcome			(XX.X%)
Resolved	XXX	(XX.X%)	XXX
Ongoing	XXX	(XX.X%)	XXX
Missing	XXX	(XX.X%)	XXX
Action taken			(XX.X%)
Nothing	XXX	(XX.X%)	XXX
Study drug dosage adjusted/temporarily interrupted	XXX	(XX.X%)	XXX
Study drug permanently discontinued due to this AE	XXX	(XX.X%)	XXX
Concomitant medication given	XXX	(XX.X%)	XXX
Non-drug therapy given	XXX	(XX.X%)	XXX
Hospitalization/prolonged hospitalization	XXX	(XX.X%)	XXX
Missing	XXX	(XX.X%)	XXX

No AEs (including SAEs) that started prior to start of treatment are included.

**TABLE 14.3-1.2 INCIDENCE OF ADVERSE EVENTS BY SYSTEM ORGAN CLASS, PREFERRED TERM, AND INTENSITY, ALL ADVERSE EVENTS (SAF)****TABLE 14.3-1.2.1 INCIDENCE OF ADVERSE EVENTS FOR OVERWEIGHT\* PATIENTS AT BASELINE BY SYSTEM ORGAN CLASS, PREFERRED TERM, AND INTENSITY, ALL ADVERSE EVENTS (SAF)**

Defined by international cut off points for BMI for overweight by sex and age at baseline. The cut-off point is defined by the percentile that passes through BMI at 25 kg/m^2 at age 18.. Programming note: Same table shell as Table 14.3-1.2 will be used.

**TABLE 14.3-1.3 INCIDENCE OF ADVERSE EVENTS BY SYSTEM ORGAN CLASS, PREFERRED TERM, AND INTENSITY, DRUG-RELATED ADVERSE EVENTS (SAF)****TABLE 14.3-1.4 INCIDENCE OF SERIOUS ADVERSE EVENTS BY SYSTEM ORGAN CLASS, PREFERRED TERM, AND INTENSITY (SAF)****TABLE 14.3-1.5 INCIDENCE OF DRUG-RELATED SERIOUS ADVERSE EVENTS BY SYSTEM ORGAN CLASS, PREFERRED TERM, AND INTENSITY (SAF)****TABLE 14.3-1.6 INCIDENCE OF NON-SERIOUS ADVERSE EVENTS BY SYSTEM ORGAN CLASS, PREFERRED TERM, AND INTENSITY (SAF)**

Novartis MedDRA version System Organ Class Preferred Term	Intensity				Total number of patients	Patients per patient years#
	Mild	Moderate	Severe	Missing		
Blood and lymphatic system disorders						

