**TABLE 14.3-1.14 INCIDENCE OF SERIOUS ADVERSE EVENTS BY SYSTEM ORGAN CLASS, PREFERRED TERM, AND OUTCOME (SAF)**

**TABLE 14.3-1.15 INCIDENCE OF DRUG-RELATED SERIOUS ADVERSE EVENTS BY SYSTEM ORGAN CLASS, PREFERRED TERM, AND OUTCOME (SAF)**

Novartis MedDRA version System Organ Class Preferred Term	Outcome				Total number of patients	Patients per patient years#
	Resolved	Ongoing	Fatal	Missing		
Blood and lymphatic system disorders						
Any AE	XX (XX.X%)	X.XXX				
Anaemia	XX (XX.X%)	X.XXX				
Eosinophilia	XX (XX.X%)	X.XXX				
Leukopenia	XX (XX.X%)	X.XXX				
Lymphadenitis	XX (XX.X%)	X.XXX				
Lymphadenopathy	XX (XX.X%)	X.XXX				
Neutropenia	XX (XX.X%)	X.XXX				
Splenomegaly	XX (XX.X%)	X.XXX				
Thrombocytopenia	XX (XX.X%)	X.XXX				
Thrombocytosis	XX (XX.X%)	X.XXX				
Cardiac disorders						
Any AE	XX (XX.X%)	X.XXX				
...	XX (XX.X%)	X.XXX				

No AEs (including SAEs) that started prior to start of treatment are included.

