**TABLE 14.3-1.18 OCCURRENCE OF SERIOUS ADVERSE EVENTS BY SYSTEM ORGAN CLASS, PREFERRED TERM, AND OUTCOME (SAF)**

**TABLE 14.3-1.19 OCCURRENCE OF DRUG-RELATED SERIOUS ADVERSE EVENTS BY SYSTEM ORGAN CLASS, PREFERRED TERM, AND OUTCOME (SAF)**

Novartis MedDRA 19.1 System organ class Preferred Term	Outcome					Events per patient year#
	Resolved	Ongoing	Fatal	Missing	Total	
	XXX	XXX	XXX	XXX	XXX	
Blood and lymphatic system disorders						X.XXX
ANY	XXX	XXX	XXX	XXX	XXX	X.XXX
Anaemia	XXX	XXX	XXX	XXX	XXX	X.XXX
Eosinophilia	XXX	XXX	XXX	XXX	XXX	X.XXX
Leukopenia	XXX	XXX	XXX	XXX	XXX	X.XXX
Lymphadenitis	XXX	XXX	XXX	XXX	XXX	X.XXX
Lymphadenopathy	XXX	XXX	XXX	XXX	XXX	X.XXX
Neutropenia	XXX	XXX	XXX	XXX	XXX	X.XXX
Splenomegaly	XXX	XXX	XXX	XXX	XXX	X.XXX
Thrombocytopenia	XXX	XXX	XXX	XXX	XXX	X.XXX
Thrombocytosis	XXX	XXX	XXX	XXX	XXX	X.XXX
Cardiac disorders	XXX	XXX	XXX	XXX	XXX	X.XXX
ANY	XXX	XXX	XXX	XXX	XXX	X.XXX
...						

No AEs (including SAEs) that started prior to start of treatment are included.

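### The SAP pools adverse events resolved with sequelae with complete resolution, so none of the nine outcome tables can identify or count them

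*SAP*

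**What the plan says.** Protocol 7.4.7 lists the outcomes that the investigator records for each adverse event. After the level for events not recovered, the list continues: "recovered/resolved; recovering/resolving, recovered/resolved with sequelae; fatal; or unknown". That makes six levels, with recovery and recovery with sequelae kept apart.

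Protocol 10.4.4 commits to tabulating outcome: "the relationship to the study drug, intensities and outcome will be shown in corresponding frequency tables". It does not say how finely the levels are to be shown.

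SAP 4.6.2.1 says that outcome is categorised according to the CRF and gives four categories: *resolved*, *ongoing*, *fatal* and *unknown*. It defines the first as "resolved completely or resolved with sequelae". The same section plans incidence and occurrence of each event "cross-tabulated with the intensity, action taken, and outcome". It also plans a listing of all adverse events in which outcome is one of the variables; this is Listing 16.2.5.1 in SAP 5.5.

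SAP section 3, on changes to planned analyses, does not mention the merging of outcome levels.

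**The concern.** The study belongs to a post-marketing pharmacovigilance plan, and its safety results will be read mainly from summary tables. The SAP gives eight tables wholly to outcome, plus a block of rows in the general summary. Followed exactly, its rule makes each of these count incomplete recovery as *resolved*. The merging can only move events in the favourable direction, and it discards a distinction that the protocol asks investigators to make. The loss extends to the tables of serious and of drug-related serious events, where a reader is most likely to ask about sequelae.

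The shells add a second problem, because they do not match the SAP's own text. The text names *fatal* and *unknown*, but not every shell has a place for them, so the programmer must decide without a written rule where those events go.

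**Working it through.** The plan gives no figure to reproduce. The check sets the outcome scales side by side.

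**Tables that show outcome**
- General summary, Table 14.3-1.1: 1 table.
- Incidence by outcome, Tables 14.3-1.12 to 14.3-1.15 (all, drug-related, serious, drug-related serious): 4 tables.
- Occurrence by outcome, Tables 14.3-1.16 to 14.3-1.19 (same four groups): 4 tables.
- Total: 1 + 4 + 4 = 9.

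**Where each protocol level goes**

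| Protocol 7.4.7 level | SAP 4.6.2.1 | Table 14.3-1.1 | Tables 14.3-1.12 to 14.3-1.19 |
|---|---|---|---|
| Not recovered | *ongoing* (most natural reading) | Ongoing | Ongoing |
| Recovered | *resolved* | Resolved | Resolved |
| Recovering | not stated | not stated | not stated |
| Recovered with sequelae | *resolved* | Resolved | Resolved |
| Fatal | *fatal* | no row | Fatal |
| Unknown | *unknown* | no row | no column |

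Every shell also has a *Missing* category.

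**What follows**
- Apart from *Missing*, six protocol levels become four categories in the SAP text, then two rows in Table 14.3-1.1 or three columns in Tables 14.3-1.12 to 14.3-1.19.
- Tables that separate sequelae from complete resolution: 0 of 9.
- In the occurrence tables, the printed count is R = R(complete) + R(sequelae). Only the sum appears, so R(sequelae) may be anything from 0 to R, and no other column helps to recover it.
- *Fatal* has a place in 8 of 9 shells and *unknown* in 0 of 9. An event with unknown outcome would have to be dropped or put under *Missing*, and no rule says which.
- The listing carries outcome, but the SAP does not say whether it prints the CRF value or the four-category value. If it prints the latter, sequelae cannot be seen in any planned adverse event output.

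**The case against.** The strongest reply is that this is a display choice, made openly. The SAP states the definition, so nothing is concealed. Protocol 10.4.4 sets no level of detail, so merged categories are not a departure from it. The adverse event objective concerns incidence and severity, which Tables 14.3-1.2 to 14.3-1.11 cover by intensity. For a category that may be rare among the 278 enrolled patients, a line listing is a reasonable way to report it. All of that stands, and it is why the point is minor. What it does not answer is that a listing gives no count or rate, and that the SAP leaves open which outcome value the listing prints.

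A second reply is that the SAP follows the CRF, which is not among the documents. That is a real limit. The SAP's own definition does name two kinds of resolution under one label, which suggests that both were recorded, but it does not prove it.

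A third is that the gaps in the shells are template matters. Table 14.3-1.1 carries a filled-in N of 277, which might indicate a shell reused from earlier output. It equally matches 278 patients less the one whom the note to Table 14.1-2 excludes from the safety set, so it settles nothing. The shells and the text still need to agree.

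A reader might infer more than the documents support:
- **That lasting harm is invisible in the outcome tables.** Deaths have a *Fatal* column in eight of the nine tables and a separate Listing 16.2.5.2. Events that never resolve, including those judged permanent, would most naturally fall under *Ongoing*, which all nine tables have. Only events marked as resolved with sequelae lose their label.
- **That sequelae means permanent damage.** The protocol neither defines nor grades sequelae.
- **That a certain number of events is affected.** The documents give neither an adverse event total nor a sequelae rate, so any count would be invented.

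**Conclusion.** The point holds as a cheap improvement in reporting. SAP 4.6.2.1 states a rule that merges two outcomes recorded separately under the protocol, and as a result none of the nine outcome tables can identify or count events resolved with sequelae. They can be found at most in the patient-level listing. Separately, Table 14.3-1.1 lacks the *fatal* row and all nine shells lack the *unknown* category that the SAP text names, and recovering events have no stated category.

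The extent in tables is certain, at nine of nine. The extent in events is unknown and may be zero; even then, a printed zero would tell the reader something that the present tables cannot. The conclusion assumes that the CRF kept the two resolved levels apart, as Protocol 7.4.7 requires. The primary endpoint and the tables by intensity and by action taken are unaffected.

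**What to change.** - In SAP 4.6.2.1, report *resolved* and *resolved with sequelae* as separate categories, and state where recovering events are counted.
- Add *resolved with sequelae* and *unknown* to all nine shells (14.3-1.1 and 14.3-1.12 to 14.3-1.19), and *fatal* to Table 14.3-1.1.
- State that Listing 16.2.5.1 prints the unmerged CRF outcome.
- If the CRF did not hold the two resolved levels separately, say so in the SAP and the report as a limitation.

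The cost is a short SAP edit, slightly larger tables and a slightly lower *resolved* count. If the CRF has both levels, no new data are needed, and no other analysis changes.

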#### **7.4.7 Adverse events**

The investigator has the responsibility for managing the safety of individual subject and identifying adverse events.

An adverse event (AE) is any untoward medical occurrence (e.g., any unfavorable and unintended sign, including abnormal laboratory findings, symptom or disease) in a subject after providing written informed consent for participation in the study until the end of study visit. Therefore, an AE may or may not be temporally or causally associated with the use of a investigational medicinal product.

In addition, all reports of intentional misuse and abuse of the product are also considered an adverse event irrespective if a clinical event has occurred.

The occurrence of adverse events should be sought by non-directive questioning of the subject at each visit during the study. Adverse events also may be identified when they are volunteered by the subject during or between visits or through physical examination, laboratory test, or other assessments.

Abnormal laboratory values or test results constitute adverse events only if they fulfill at least one of the following criteria:

- they induce clinical signs or symptoms,
- the investigator considers them to be clinically relevant,
- they require therapy.

Clinically relevant abnormal laboratory values or test results should be identified through a review of values outside of normal ranges/clinically notable ranges, relevant changes from baseline or the previous visit, or values which are considered to be non-typical in subject with underlying disease.

Adverse events must be recorded on the adverse events CRF with the following information within 10 days of learning of its occurrence (if the event is serious (refer to Section 7.4.8) it must be recorded in the CRF within 24 hours of learning of its occurrence):

- the severity grade (indicating most severe grade during the course of the adverse event)
  - mild: usually transient in nature and generally not interfering with normal activities
  - moderate: sufficiently discomforting to interfere with normal activities
  - severe: prevents normal activities
- its relationship to the study drug(s) (suspected/not suspected)
  - Not suspected: The temporal relationship of the clinical event to trial drug administration makes a causal relationship unlikely, or other drugs, therapeutic interventions or underlying conditions provide a sufficient explanation for the observed event.

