### **4.4 Treatment regimen, compliance and exposure to drug**

The patient's exposure to study drug will be calculated from the date of first dose to the date of last study drug administration for patients that prematurely discontinued or completed the study, and presented in years as a decimal.

If date of last study drug administration is missing completely or only a year is given and the patient has discontinued or completed the study, then the date the patient discontinued or completed the study shall be used instead. If date of last study drug administration was given only partial (i.e. month and year given), the first date of the month will be assumed as last administration date. Study drug exposure in days will be converted to study drug in years as follows:

- Exposure (years) = Exposure (days)/365.25.

The patient's exposure to study drug will also be summarized by site for FAS.

The total daily dose administered per kg body weight will be summarized by visit to assess the appropriateness of the applied dose for FAS.

A summary table providing the number and percentage of patients with any study drug dose change documented by reason for dose change overall and by number of times the respective reason was documented per patient will be provided. As for some patients dose change records

were documented when the patient returned to the recommended dose, all records with a daily dose of 0.035 mg/kg will be excluded from the summary tables.

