# Patient years = XXX.XXX

Patient years are calculated as years of exposure (i.e. total sum of the number of years that each patient was treated).

**TABLE 14.3-1.7 OCCURRENCE OF ADVERSE EVENTS BY SYSTEM ORGAN CLASS, PREFERRED TERM, AND INTENSITY, ALL ADVERSE EVENTS (SAF)**

**TABLE 14.3-1.8 OCCURRENCE OF ADVERSE EVENTS BY SYSTEM ORGAN CLASS, PREFERRED TERM, AND INTENSITY, DRUG-RELATED ADVERSE EVENTS (SAF)**

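### Minor: the per-patient-year column in the AE incidence tables counts each child once but keeps adding treated years after the first event; a row-specific time at risk is a cheap improvement

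*SAP*

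**What the plan says.** SAP 4.6.2.1 defines AE incidence as patients with the event over patients in the SAF. It adds: "With AE incidence, each event will be counted only once for a given patient". For class rows: "Incidence of events within a system organ class is defined similarly". For the rate column: "Incidence tables will provide information about rates of AEs per patient-year, calculated as" patients with the event over years of exposure.

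In SAP 5.4 the column is headed "Patients per patient years", and the footnote reads: "Patient years are calculated as years of exposure (i.e. total sum of the number of years that each patient was treated". One patient-year total is printed for the whole table. This applies to 14 incidence tables on three shells: 14.3-1.2 to 1.6 (including 1.2.1), 1.12 to 1.15, and 1.20 to 1.23.

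The two periods are set in different places:
- **Exposure (SAP 4.4):** "exposure to study drug will be calculated from the date of first dose to the date of last study drug administration".
- **AEs before treatment (SAP 4.6.2.1):** "AEs starting prior to start of treatment will not be included in the summary tables, but listed only".
- **AE collection (Protocol 7.4.7):** "in a subject after providing written informed consent for participation in the study until the end of study visit". Protocol 8.1 takes SAE reporting to 30 days after the last administration.

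The occurrence tables divide all events by the same years of exposure. That denominator suits a count that includes repeat events.

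**The concern.** A child stops contributing to the numerator after one event but goes on contributing years to the denominator. Two groups with the same underlying risk but different lengths of treatment would therefore show different values.

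The documents suggest that treatment is long and unequal. On 31-Dec-2019, 32 children were still treated although the last enrolment was on 29-Apr-2010, so each had been enrolled for at least about 9.7 years. Other children may stop after the first year for inadequate response.

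Incidence of adverse events is a secondary objective. This column is the only planned time-based figure for patients affected: the SAF percentages ignore length of treatment, and the occurrence rates mix repeat events with newly affected children. What is at stake is how a descriptive column is read, mainly for common terms and class rows.

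**Working it through.** **Inputs.** The plan states no AE rate or patient-year total, so there is no figure to reproduce. The SAF size can be checked: 278 treated (SAP 4.8) minus the one patient excluded in the note to Table 14.1-2 gives 277, as printed in the shell of Table 14.3-1.1. Hazards and exposure lengths below are assumptions.

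**Formula.** The column is k / ΣT, where k is patients affected and T is treated time. The first-event rate is k / Σmin(t, T), where t is time to first onset. With constant hazard, equal T and proportion affected p, the ratio of the column to the first-event rate is p / (−ln(1−p)).

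| p | Children of 277 | Ratio | Shortfall |
|---|---|---|---|
| 1% | 3 | 0.995 | 0.5% |
| 5% | 14 | 0.975 | 2.5% |
| 10% | 28 | 0.949 | 5% |
| 20% | 55 | 0.896 | 10% |
| 50% | 139 | 0.721 | 28% |
| 80% | 222 | 0.497 | 50% |

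**Worked example.** Assume 7 treated years each: 277 × 7 = 1,939 patient-years.
- 28 children: column 28/1,939 = 0.0144; first-event rate 0.0152.
- 139 children: column 139/1,939 = 0.0717; first-event rate −ln(1 − 139/277)/7 = 0.0995.
- 222 children: column 222/1,939 = 0.1145; first-event rate 0.2310.

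**Dependence on treatment length.** Hold the hazard at 0.10 per year. The column is (1 − e^(−0.10T))/T:
- 4 years: 0.3297/4 = 0.0824
- 7 years: 0.5034/7 = 0.0719
- 10 years: 0.6321/10 = 0.0632

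**Unequal exposure.** Take exposure uniform from 1 to 11 years (mean 6) and hazard 0.10. Then p = 1 − (e^(−0.1) − e^(−1.1))/(0.1 × 10) = 0.428. The column is 0.428/6 = 0.0713, 29% low, against 23% from the equal-exposure formula.

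**Events after the last dose.** Suppose onsets count until 30 days (0.0821 year) after the last dose, hazard 0.10.
- One year of exposure: (1 − e^(−0.10 × 1.0821))/1 = 0.1026, about 3% high.
- Six years: (1 − e^(−0.10 × 6.0821))/6 = 0.0759, against 0.0752 without post-dose events. The column is still about 24% low.

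**Check of the fix.** A simulation of 2,000,000 children with the same 30-day tail and a true rate of 0.10 applied the time at risk proposed below. It returned 0.1003 at one year, 0.0999 at six years and 0.1000 for uniform 1–11 years. At one year, ending time at first onset while still counting post-dose onsets gave 0.1081, 8% high. The numerator must therefore be confined to the same window.

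**The case against.** The strongest reply is that nothing here is wrong as printed. The text, the footnote and the column heading agree, and the SAP never calls the column a first-event rate. That stands: this is a better choice of descriptive ratio, not the repair of an error.

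Several stronger readings are tempting, and the documents do not support them:
- **That reported AE incidence is understated.** The SAP defines incidence as a percentage of the SAF, which does not change.
- **That the diabetes result is affected.** Table 14.3-3.7 gives counts and percentages only.
- **That the column is always low.** With short exposure, post-dose onsets can make it slightly high.
- **That AE counting has no end.** SAP 4.6.2.1 covers the whole study period, and Protocol 7.4.7 and 8.1 set the limits. What remains is a short mismatch with exposure, about 1% of the column in the six-year example.

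Two practical objections also deserve an answer. First, ending time at the first onset of a term regardless of table would be wrong in the ten tables restricted to drug-related, serious, drug-related serious or non-serious events. A child with a non-serious event in year 1 and a serious one of the same term in year 5 would drop out of the serious-event rate. Second, the date rules can collide: SAP 4.7 puts an unknown AE day on the 15th, while SAP 4.4 puts an unknown last-dose day on the first of the month. Both points stand, and the fix below allows for them.

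A common denominator also lets a reader divide the occurrence rate by the incidence rate to get events per affected child. That convenience goes, but the same figure follows from the counts in the two sets of tables.

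**Conclusion.** The point holds as a minor improvement. The column is a valid ratio whose value depends on length of treatment. With multi-year exposure it falls below the first-event rate for common terms and class rows, by the amounts tabulated, under constant hazard and equal exposure. Unequal exposure widened the gap in the case examined. For rare terms the difference is negligible.

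How large the gap will be here cannot be determined, because neither AE frequencies nor mean exposure are given. The 28% and 50% figures apply only if half or four-fifths of children are affected in a row. No test, decision or primary conclusion rests on the column.

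**What to change.** Amend SAP 4.6.2.1 for the 14 incidence tables:

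1. **Time at risk.** For each row, use time from first dose to the earlier of (a) the first on-treatment onset of an event that qualifies for that table and row, and (b) end of exposure under SAP 4.4. Qualifying means the first serious onset in serious-AE tables, the first drug-related onset in drug-related tables, and the first qualifying event of any term in the class for Any AE rows.
2. **Numerator.** Count in the rate only qualifying first onsets within that time. Footnote rows where this differs from the patient count.
3. **Partial dates.** Complete onset dates by SAP 4.7, with two limits. A completed date may not fall before first dose when the event is known to have started on treatment. It may not fall after end of exposure when only the imputed days cause that.
4. **Display.** Show row-specific patient-years in their own column and change the footnote on all three incidence shells. Keep total exposure in the occurrence tables, and keep the SAF percentages.

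The cost is a few SAP sentences, three footnotes and one programmed denominator rule, using AE start dates and dosing dates already collected. The downsides are denominators that vary by row, an extra column, and incidence and occurrence rates that no longer share a denominator. If the sponsor declines, the minimum is a footnote saying that time is not ended at the first event and how onsets after the last dose are counted.

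Secondary: SAP 4.6.2.1 promises formulation-specific AE rates without a window, and the table list names no such table. If they are produced, use the first-twelve-month window of Protocol 10.9 by initial formulation, because once-per-patient rates over unequal windows are not comparable.
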